13.3. Safety Laboratory Data

The summary statistics (including number, mean, median, SD, minimum and maximum) of all safety laboratory tests (ie. hematology and chemistry panels) will be calculated for each visit (baseline and post-baseline time points) and presented by treatment group.

Shift tables reflecting changes from baseline (i.e., normal to low, high, etc.) will be presented in lieu of descriptive statistics of changes from baseline. Listings of subjects with laboratory values that are out of the reference range will be produced.

Potential drug-induced liver injury

The liver function tests, namely ALT, AST, ALP (alkaline phosphatase), and TBL (total bilirubin), will be used to assess possible drug-induced liver toxicity.

A graph of distribution of peak values of ALT versus peak values of TBL will be presented. Note that the ALT and TBL values are presented on a logarithmic scale. The graph will be divided into 4 quadrants with a vertical line corresponding to $3 \times$ ULN for ALT and a horizontal line corresponding to $2 \times$ ULN for TBL.

The number of subjects with elevated liver function tests will be summarized in a table by categories of elevation ($3 \times$ ULN, $5 \times$ ULN, $10 \times$ ULN, $20 \times$ ULN for ALT and AST, $1.5 \times$ ULN for ALP, and $1.5 \times$ ULN and $2 \times$ ULN for TBL), along with the following categories of normalization (to $\leq 1 \times$ ULN or return to baseline if baseline $>$ ULN): never normalized,

normalized after permanent discontinuation of study drug. Note that a patient will be counted only under the maximum elevation category (1-3 \times ULN, 3-5 \times ULN, 5-10 \times ULN, 10-20 \times ULN, $>$ 20 \times ULN).

If identified, the number of subjects with concurrent ALT/AST of 3 \times ULN or higher, TBL of 2 \times ULN or higher, and ALP below 2 \times ULN (possible Hy's Law cases) will also be summarized in this table and included in a by-subject listing as well.

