#### **7.4.2        *Criteria for Conditional Withholding of Study Drug Due to Potential Hepatotoxicity***

For participants who do not meet the criteria for permanent withholding of study medication outlined above, study drug should be withheld if ANY of the following criteria are met, and the participant should be evaluated for DILI:

- Elevation of either AST or ALT, regardless of baseline AST or ALT value, if:
  - $> 8 \times \text{ULN}$  at any time
  - $> 5 \times \text{ULN}$  and  $< 8 \times \text{ULN}$  for  $\geq 2$  weeks
  - $> 5 \times \text{ULN}$  and  $< 8 \times \text{ULN}$  and unable to adhere to enhanced monitoring schedule
- OR: clinical signs or symptoms that are, in the opinion of the investigator, consistent with hepatitis (such as right upper quadrant pain/tenderness, fever, nausea, vomiting, jaundice, rash or eosinophilia  $> 5\%$ ). If such signs or symptoms are coupled with ALT or AST elevations  $> 3 \times \text{ULN}$ , study medication should be withheld
- OR: TBL  $> 3 \times \text{ULN}$  at any time
- OR: ALP  $> 8 \times \text{ULN}$  at any time

Study drug should be withheld pending an investigation into alternative causes of DILI. If study medication is withheld, the participant should be followed according to recommendations in [APPENDIX 3](#) for possible DILI. Rechallenge may be considered if an alternative cause, such as acute hepatitis B infection, is discovered and the laboratory abnormalities resolve to normal or baseline ([Section 7.4.3](#)).

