12.3.8.1 Adverse Events

AEs will be mapped to system organ classes and preferred terms using the Medical Dictionary for Regulatory Activities (MedDRA). AEs will be monitored during the study and the data analyzed with respect to overall incidence as well as severity and potential relationship of AEs to study medication. AEs with onset during the treatment-emergent period or with an onset before the first dose of study medication that increases in severity or becomes serious during the treatment-emergent period, will be considered treatment-emergent.

Adverse event incidence tables will present the number (n) and percentage (%) of participants experiencing at least one treatment-emergent AE (TEAE) by system organ class (SOC) and preferred term (PT). Multiple occurrences of the same event in the same participant will be counted only once in the tables. The denominator for computation of percentages is the safety population within each treatment group.

Adverse event incidence tables will be provided by treatment group for all types of TEAEs: all TEAEs, all treatment-emergent SAEs and all TEAEs leading to permanent treatment discontinuation.

*Potential drug-induced liver injury*

The incidence of liver-related AEs will be summarized by treatment group. The selection of PTs will be based on standardized MedDRA query hepatic disorder.

*Deaths*

The following deaths summaries will be generated:

- Number and percent of participants who died by study period (TEAE, on-study) summarized on the safety population by treatment received
- Death in non-randomized participants or randomized and not treated participants
- TEAE leading to death (death as an outcome on the AE eCRF page as reported by the investigator) by primary SOC and PT showing number and percent of participants

*Pregnancy*

The following pregnancy summaries will be generated:

- Number of participants or partners of participants who became pregnant summarized by treatment received
- Outcomes of the pregnancies and analysis of the outcomes

- TEAE experienced during the pregnancy by primary SOC and PT showing the number and percent of participants

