13.1. Adverse Events

AEs will be mapped to system organ classes and preferred terms using the Medical Dictionary for Regulatory Activities (MedDRA v21.0). AEs will be monitored during the study and the data analyzed with respect to overall incidence as well as severity and potential relationship of AEs to study medication. AEs with onset during the treatment-emergent period or with an onset before the first dose of study medication that increases in severity or becomes serious during the treatment-emergent period, will be considered treatment-emergent.

Adverse event incidence tables will present the number (n) and percentage (%) of subjects experiencing at least one treatment-emergent AE (TEAE) by system organ class (SOC) and preferred term (PT). Multiple occurrences of the same event in the same patient will be counted only once in the tables. The denominator for computation of percentages is the safety population within each treatment group. In addition, the adverse event incident table will also be presented by SOC, PT, and severity grade. When there are multiple occurrences of the same event in the same patient, only the most severe one will be included in the tables.

Adverse event incidence tables will be provided by treatment group for all types of TEAEs: all TEAEs, all treatment-emergent serious AEs, drug related AEs, AEs of Special Interest (AESI; per protocol), all TEAEs leading to permanent treatment discontinuation, and all TEAEs leading to death.

AE may also be summarized by Standardised MedDRA Queries (SMQs) deemed relevant based on AESIs and SAEs observed in the study.

A by-subject listing of all AEs, SAEs, and TEAEs leading to treatment discontinuation will also be provided.

Deaths

The following deaths summaries will be generated in a summary table and listed in a by-subject data listing:

- Number and percent of subjects who died by study period (TEAE, on-study) summarized on the safety population by treatment received
- Death in non-randomized subjects or randomized and not treated subjects
- TEAE leading to death (death as an outcome on the AE eCRF page as reported by the investigator) by primary SOC and PT showing number and percent of subjects

Pregnancy

The following pregnancy information will be provided in a by-subject data listing:

- Number of subjects or partners of subjects who became pregnant summarized by treatment received
- Outcomes of the pregnancies and analysis of the outcomes

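### The SAP's liver table names bilirubin and ALP cut-offs that its own counting rule hides, and it has no recovery category for participants who normalize without permanently stopping drug

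*SAP*

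**What the plan says.** The liver-injury part of SAP 13.3 specifies one table of elevated liver tests. It names levels of 3, 5, 10 and 20 × ULN for ALT and AST, 1.5 × ULN for ALP, and 1.5 and 2 × ULN for TBL. Normalization means reaching ≤ 1 × ULN, or returning to baseline if baseline was above ULN. There are two outcomes: the test never normalized, or it was "normalized after permanent discontinuation of study drug. Note that a patient will be counted" (the quote runs on into the counting rule). The rule continues "only under the maximum elevation category" and lists 1-3, 3-5, 5-10, 10-20 and > 20 × ULN.

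Protocol 12.3.8.3 has the same levels, bins and outcomes, so the SAP inherited them. The SAP adds a row for possible Hy's Law cases: ALT/AST at least 3 ×, TBL at least 2 × and ALP below 2 × ULN, all together.

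Two neighbouring provisions matter less:

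- **Laboratory scope.** SAP 13.3 says summary statistics of "all safety laboratory tests (ie. hematology and chemistry panels) will be calculated for each visit". Coagulation is not named.
- **Liver adverse events.** Protocol 12.3.8.1 commits to a summary by treatment group and adds: "The selection of PTs will be based on standardized MedDRA query hepatic disorder". The readable part of SAP 13.1 says only: "AE may also be summarized by Standardised MedDRA Queries (SMQs) deemed relevant based on AESIs and SAEs observed in the study".

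**The concern.** The list of cut-offs and the counting rule sit in one paragraph and disagree for TBL and ALP. A programmer must set one of them aside, and the SAP does not say which. If the counting rule wins, the table loses TBL 2 × ULN, which the protocol itself uses as its bilirubin threshold in 7.4.1 and Appendix 3.

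The recovery outcomes omit courses that the protocol expects. Protocol 10.1.1 treats any interruption as temporary at first unless the protocol requires permanent discontinuation. Protocol 7.4.2 says "Rechallenge may be considered if an alternative cause, such as acute hepatitis B infection, is discovered and the laboratory abnormalities resolve to normal or baseline", which presupposes recovery without permanent discontinuation.

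Safety and tolerability is the primary objective (SAP 2.1), and the frequency of laboratory abnormalities is a listed safety endpoint (SAP 6.1). These tables therefore bear on what the trial is meant to describe.

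**Working it through.** The plan states no figure for these tables, so there is none to reproduce. The check sets each cut-off named in SAP 13.3 against the bins in the same paragraph. A count above a cut-off can be recovered from the bins only if the cut-off is a bin edge.

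| Test | Cut-off (× ULN) | Position in the bins |
|---|---|---|
| ALT/AST | 3 | edge of 1-3 and 3-5 |
| ALT/AST | 5 | edge of 3-5 and 5-10 |
| ALT/AST | 10 | edge of 5-10 and 10-20 |
| ALT/AST | 20 | edge of 10-20 and > 20 |
| ALP | 1.5 | inside 1-3 |
| TBL | 1.5 | inside 1-3 |
| TBL | 2 | inside 1-3 |

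All four ALT/AST cut-offs are edges, so those counts work. The shared edges still need inequality signs, since 3 belongs to both 1-3 and 3-5.

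For TBL, take four participants in one arm with the same peak value and apply the rule literally:

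| Peak TBL (× ULN) | Row over the five bins | True count > 1.5 × | True count > 2 × |
|---|---|---|---|
| 1.2 | 4, 0, 0, 0, 0 | 0 | 0 |
| 1.6 | 4, 0, 0, 0, 0 | 4 | 0 |
| 2.4 | 4, 0, 0, 0, 0 | 4 | 4 |

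Three different safety pictures give one row. In general, if k participants fall in the 1-3 bin and m in the higher bins, the number above 2 × ULN can be anything from m to m + k. The same holds for ALP at 1.5 × ULN. With about 20 participants per arm (SAP 5), the example's four are 4/20 = 20% and one participant is 1/20 = 5 percentage points. That is the scale of the table, not an estimate of how many will be affected.

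Recovery courses against the two outcomes:

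- Never normalizes: has a place.
- Normalizes after permanent discontinuation: has a place.
- Normalizes while still on drug: none.
- Normalizes during or after a temporary hold (Protocol 7.4.2, 7.4.3, 10.1.1): none.
- Normalizes after completing treatment: none on the ordinary reading, because Protocol 10.1.4 describes permanent discontinuation as occurring before Week 16.

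On INR, Protocol 7.4.1 requires TBL > 2 × ULN or INR > 1.5, together with AST or ALT > 3 × ULN from a baseline below ULN and no other apparent cause. The Hy's Law row has no INR route. A participant with ALT > 3 × ULN, INR > 1.5 and TBL below 2 × ULN could meet the laboratory part of 7.4.1 without appearing in that row.

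**The case against.** The best reply on the bins is that they mirror the ALT/AST cut-offs, so the note may be only a no-double-counting rule for those two tests. The named TBL and ALP levels would then stand as their own categories. That reading is reasonable and is probably the intention, but the note is not limited to ALT and AST, so the text needs to say so.

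Other outputs also show some of the information. The peak ALT-TBL plot has a line at TBL 2 × ULN, out-of-range values are listed, and possible Hy's Law cases have their own row and listing. This stands, and it limits the loss. It does not supply the named counts: SAP 13.3 does not say that the plot is by arm, listings are not counts, and the Hy's Law row excludes isolated TBL or ALP elevation.

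A reader might infer that INR is left out of the analysis. The documents do not establish that. Protocol Appendix 1 lists INR as a safety laboratory parameter in a combined hematology and coagulation column, an out-of-range INR would be listed, and SAP 13.6 counts participants meeting each stopping criterion. Against this, the schedule gives the coagulation panel its own row, and INR is not among the liver tests named in SAP 13.3. The scope is unclear rather than shown to be missing. A stand-alone INR > 1.5 row would not match 7.4.1 either, and it would pick up anticoagulant effect, since exclusion criterion 9 allows anticoagulated participants with atrial fibrillation.

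A reader might also infer that the SAP dropped the hepatic query without declaring it. SAP 13.1 does not cancel the protocol's analysis, its query sentence is worded as an addition, and SAP 16, on changes from the protocol, is not readable. All treatment-emergent events are tabulated by system organ class, preferred term and severity in any case. What remains is that the readable SAP text has only an optional query chosen from observed events. None of the events of special interest in Protocol 11.2.1.3 is hepatic, so non-serious liver events alone would not prompt it.

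**Conclusion.** The point holds for TBL and ALP and for the recovery outcomes. Applied literally, the counting rule puts all three TBL and ALP cut-offs in one bin, and the by-arm counts cannot be recovered from the table. Three ordinary recovery courses have no category. The first conclusion assumes that the note covers every liver test. The second does not depend on that reading, although its third course assumes the ordinary meaning of permanent discontinuation.

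It would go too far to say that the liver tables fail in general, because the ALT and AST counts work. Nor do the documents say that participants who recover on drug will be put in a wrong row; they simply give no rule. Laboratory abnormalities are listed as a safety endpoint, and only the objective is called primary.

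The effect is confined to descriptive safety tables. SAP 13 plans no hypothesis testing for safety, and the sample size is untouched. The coagulation and hepatic-query points are secondary clarifications.

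**What to change.** In SAP 13.3:

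- Limit the listed bins to ALT and AST, with inequality signs at the shared edges.
- For TBL use maximum categories of > 1.5 to 2 × ULN and > 2 × ULN; for ALP use > 1.5 × ULN.
- Add three recovery outcomes: normalized on study drug, normalized during or after temporary withholding, and normalized after completing treatment.
- State that coagulation tests are among the summarised safety laboratory tests. If INR > 1.5 is counted, count it jointly with ALT/AST > 3 × ULN, as Protocol 7.4.1 does, and flag anticoagulant use.

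In SAP 13.1, carry over the protocol's hepatic-disorder query as a fixed table by treatment group, and label any query chosen from observed events as post hoc.

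The cost is SAP wording and table shells. The laboratory and adverse-event data are already collected under the schedule, and nothing changes in trial conduct or treatment rules.

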13.4. Vital Signs Data

The summary statistics (including number, mean, median, SD, minimum and maximum) of all vital signs variables (values and changes from baseline) will be calculated for each visit (baseline and post-baseline time points) and presented by treatment group.

Shift tables reflecting changes from baseline may be presented in lieu of descriptive statistics of changes from baseline.

13.5. Cardiac Rhythm Monitoring (including Holter Monitor)

The summary statistics (including mean, median, SD, minimum and maximum) of atrial fibrillation (AF), nonsustained ventricular tachycardia (NSVT) will be calculated for each visit (baseline and post-baseline time points) and presented by treatment group. For each cardiac event type, the number of subjects with at least one occurrence, the number of episodes per subject per day, and the duration of each episode will also be summarized. Additional parameters may be summarized as appropriate.

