### **5.3                   Exclusion Criteria**

A participant who meets any of the following criteria will be excluded from the study.

1. Previously participated in a clinical study with mavacamten
2. Hypersensitivity to mavacamten or any of the components of the mavacamten formulation
3. Participated in a clinical trial where the participant received any investigational drug (or is currently using an investigational device) within 30 days prior to Screening or 5 times the respective elimination half-life (whichever is longer)
4. Has a known infiltrative or storage disorder causing cardiac hypertrophy that mimics nHCM, such as Fabry disease, amyloidosis, or Noonan syndrome with LV hypertrophy
5. Has any medical condition that precludes upright exercise stress testing
6. Has a history of syncope or a history of sustained ventricular tachyarrhythmia with exercise within the past 6 months
7. Has a history of resuscitated sudden cardiac arrest at any time or known appropriate implantable cardioverter defibrillator (ICD) discharge within 6 months prior to Screening
8. Has paroxysmal, intermittent atrial fibrillation with atrial fibrillation present per the investigator's evaluation of the participant's electrocardiogram (ECG) at the time of Screening
9. Has persistent or permanent atrial fibrillation not on anticoagulation for at least 4 weeks prior to Screening and/or is not adequately rate-controlled within 6 months prior to

Screening (note: patients with persistent or permanent atrial fibrillation who are anticoagulated and adequately rate-controlled are allowed)

10. Is currently treated with disopyramide or ranolazine (within 14 days prior to Screening) or treatment with disopyramide or ranolazine is planned during the study
11. For participants on beta blocker, verapamil, or diltiazem, any dose adjustment < 14 days before Screening (see [Section 7.7.2](#))
12. Currently treated or planned treatment during the study with a combination of beta blocker and verapamil or a combination of beta blocker and diltiazem
13. Has been treated with invasive septal reduction (surgical myectomy or percutaneous alcohol septal ablation) within 6 months prior to Screening (note: if a participant has had prior septal reduction therapy, the diagnostic wall thickness criteria and all other eligibility criteria must be met at time of Screening)

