6. GENERAL STATISTICAL CONSIDERATIONS

The primary analysis will be conducted through the 16-week treatment period. Data collected through this timepoint will be cleaned and locked prior to analysis.

Once all subjects have completed their Week 24/EOS visit, all data will be cleaned and locked, and analyses using this data will be used to inform study objectives relating to follow-up safety and reversibility of drug effect.

SAS® version 9.4 or higher will be used for statistical analyses, tabulations and graphical presentations.

In general, descriptive summaries will be presented by treatment group [placebo, Group 1, Group 2, and overall active]. Summaries of continuous variables will utilize the number of subjects (N), mean, standard deviation (SD), median, minimum and maximum. Descriptive summaries for categorical variables will utilize counts and percentages. Unless otherwise stated, denominators for percentages will be the number of patients in the analysis population with non-missing variable of interest for the column of interest.

The between-group comparisons focus on the comparative performance of Group 1 (target concentration of ~200 ng/mL) vs placebo and Group 2 (target concentration of ~500 ng/mL) vs

placebo. An overall active vs placebo comparison will also be conducted where appropriate. Any statistical test will be conducted at a two-sided significance level of 0.05 using the exact method unless otherwise stated.

In general, baseline is defined as the last non-missing result on or before the first dose date, and time where applicable. For certain data types (e.g., accelerometer, PROs, cardiac rhythm monitoring, etc.), special considerations may be required; please refer to the specific data section for details. Unless otherwise noted, non-safety (ie. efficacy, PD) information displayed “by visit” will utilize analysis visits as defined by the analysis visit window as opposed to the visits at which the information was collected (ie. nominal visit). Data collected at unscheduled or early termination visits will also be mapped to analysis visits. The analysis day for purposes of the visit windows are derived as follows (reference date is the study drug initiation date for the safety population or the randomization date for the ITT population):

- If date of information is missing, analysis day cannot be calculated and leave as missing
- If date of information < reference date, analysis day = analysis date – reference date.

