6.1. Study Endpoints

Safety Endpoints:

- Frequency and severity of treatment-emergent AEs, AEs of special interest, and SAEs
- Frequency of laboratory abnormalities
- Change from baseline vital signs
- Frequency of cardiac rhythm abnormalities

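### The planned patch summaries in SAP 13.5 show atrial fibrillation before and on treatment by arm but do not cross the two, so they bound new cases without identifying them when baseline fibrillation is intermittent or converts

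*SAP*

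**What the plan says.** **Endpoint.** SAP 6.1 lists "Frequency of cardiac rhythm abnormalities" as a safety endpoint.

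**Planned summary.** SAP 13.5 gives summary statistics for AF and non-sustained ventricular tachycardia at baseline and post-baseline time points by treatment group. For each event type it adds "the number of subjects with at least one occurrence, the number of episodes per subject per day, and the duration of each episode". It closes with "Additional parameters may be summarized as appropriate".

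**Baseline.** SAP 6 names rhythm data among the types that might need their own baseline rule: "cardiac rhythm monitoring, etc.), special considerations may be required; please refer to the specific data section for details". Section 13.5 contains no such rule. The general safety rule in SAP 13 takes the last value available before the first dose.

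**Who may enter with AF.** Protocol 5.3, exclusion 9, notes that "patients with persistent or permanent atrial fibrillation who are anticoagulated and adequately rate-controlled are allowed". Exclusion 8 bars a person who "Has paroxysmal, intermittent atrial fibrillation with atrial fibrillation present per the investigator's evaluation" of the Screening ECG. Paroxysmal AF that is not on that ECG is therefore eligible.

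**Data.** Under Protocol 9.3.4 and Table 1 (footnote m), patches are worn in two periods: one starting in Screening and one starting at Week 12. Two sequential patches give about 14 days of recording, which a core laboratory analyses.

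**Comparator.** For "Frequency of laboratory abnormalities", the other endpoint worded this way, SAP 13.3 commits to a within-participant display: "Shift tables reflecting changes from baseline (i.e., normal to low, high, etc.) will be presented".

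**The concern.** In a trial whose objective is safety, a reader of the rhythm table will want to know how many participants developed AF on study drug. Some participants may legitimately enter with AF. A count of participants with AF during the Week 12 to 16 patch period then mixes people who brought AF with them and people who acquired it. Placing the baseline count in the next column helps, but two separate totals do not show whether the same people are in both.

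At stake is the clarity of one descriptive safety table. Protocol 9.3.4 says the patch is there to look at rhythm before and during treatment. That is a within-participant question, and the planned table answers it only at group level.

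**Working it through.** **Plan's own figure.** SAP 5 gives about 20 per arm in 3 arms: 3 × 20 = 60, as stated. The documents give no AF prevalence or onset rate, so every AF count below is an assumption. Each participant is assumed to have both recordings.

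**Notation for one arm.** n = participants; B = those with AF at baseline; T = those with AF on treatment; R = baseline cases seen in AF again on treatment. SAP 13.5 reports B and T but not R.

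- New cases = T − R.
- The lowest value is max(0, T − B), when as many baseline cases as possible recur.
- The highest value is min(T, n − B), when as few as possible recur.

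**One arm, n = 20, B = 4, T = 4.**
- Lowest: max(0, 4 − 4) = 0. Highest: min(4, 16) = 4.
- As a share of the 20 − 4 = 16 free of AF at entry: 0/16 = 0% to 4/16 = 25%.

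**Two arms, n = 20 and B = 4 in each, T = 4 and T = 6.**

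| Assumption on baseline cases | New, arm with T = 4 | New, arm with T = 6 | Difference in new cases |
|---|---|---|---|
| Any number recur (R from 0 to 4) | 0 to 4 | 2 to 6 | 2 − 4 = −2 to 6 − 0 = +6 |
| At least two per arm recur (R from 2 to 4) | 0 to 2 | 2 to 4 | 2 − 2 = 0 to 4 − 0 = +4 |
| All recur (R = 4) | 0 | 2 | +2 |

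The second row would apply if two of the four baseline cases in each arm had permanent AF. In the third row the difference in new cases equals the difference in the reported counts, 6 − 4 = 2.

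**When the two totals are enough.** They fix the number of new cases if B = 0, T = 0, B = n or T = n, or if all baseline AF is known to recur. Otherwise they give a range. The range comes from baseline AF that is intermittent or converts. A table crossing baseline with on-treatment status reports R directly and replaces each range with one number per arm.

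**Reading of 13.5.** The sentence with the participant counts does not repeat that they are given by visit. By-visit counts are the natural reading and are assumed here. If the counts were not by visit, the gap would be wider.

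**The case against.** **Adverse event tables already separate new from prior AF.** SAP 13.1 counts events that start, or earlier events that worsen, in the treatment-emergent period. Table 1 footnote d has changes after dosing recorded as adverse events, and Protocol 11.1.1 asks for clinically important abnormalities that are new or worsening. The window runs to 56 days after the last dose, well beyond one patch period, and investigators review ECGs at Weeks 4, 8, 12, 16 and 24. This stands for AF that is reported. It does not cover AF seen only on the patch. Protocol 9.3 ties recording of abnormal findings to the investigator's view of clinical importance. Section 11.1.1.1 leaves out abnormal assessments associated with the underlying disease unless more severe than expected. The readable text does not say whether core-laboratory patch results go back to the site, so the size of this remainder is unknown.

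**The ranges are extreme.** Four new cases with 4 of 20 at both times would need every baseline case to be free of AF throughout the on-treatment recording. Permanent AF would not behave that way. This stands: the figures are outer bounds.

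**The endpoint is frequency, not onset.** This also stands. Section 13.5 does report frequency by time point and arm, and shift tables are only optional for vital signs (SAP 13.4). The laboratory comparison shows that the sponsor uses such displays, not that one is required here.

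**The open-ended sentence allows the extra table.** It does, but it commits to nothing.

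**Two stronger inferences fail.**
- A reader might infer that the trial cannot tell new AF from old. The paired recordings exist, so the limit lies in the planned 13.5 tables only.
- A reader might infer that counting everyone with AF dilutes a real difference between arms. Take new-onset AF of 5% v 20%, with 20% in AF at baseline in both arms and all of it persisting. The on-treatment counts are then 24% v 36%. But the baseline column is also reported: (0.24 − 0.20)/0.80 = 0.05 and (0.36 − 0.20)/0.80 = 0.20. The true rates are recovered exactly.

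**Conclusion.** The point holds for the patch summaries planned in SAP 13.5. Because the protocol admits participants with AF, those tables bound new AF on treatment but do not identify it when some baseline AF is intermittent or converts. In the illustration the bound is 0 to 4 new cases in an arm of 20. The assumed counts set that size, and any permanent AF among the baseline cases would narrow it.

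The consequence is a less informative descriptive table. Safety is analysed without hypothesis testing (SAP 13), so no test, alpha or power is affected. If nobody has AF at baseline, nothing is lost. This is a cheap improvement rather than an error that threatens the trial's conclusions.

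**What to change.** In SAP 13.5:

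1. Define baseline AF status from medical history, the Screening ECG and the whole Screening patch record. This also supplies the rhythm-specific baseline rule to which SAP 6 refers.
2. Add, by arm, a shift table of AF status at baseline against AF status on the Week 12 to 16 patch.
3. From that table, report new-onset AF among participants free of AF at baseline, stating the denominator.

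**Cost.** SAP wording, one derived variable and one more descriptive table, all from data already collected. The new-onset denominator is slightly smaller than the arm. The definition is best fixed before unblinding, so that it is not chosen with the results in view.
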